6. SUBJECT DISPOSITION

A listing of all Screen Failures (i.e., subjects who were screened but not randomized) will be presented along with reasons for screen fail and details of any adverse events (AEs).

The number of subjects included in each analysis set (i.e., Screened, Randomized, Safety, FAS) will be summarized by treatment group (SHP465 6.25 mg or Placebo) and overall, except for the Screened Set, which will be summarized only overall.

The number and percentage of subjects who completed and prematurely discontinued during the Treatment period will be presented for each treatment group and overall for the Safety Set. Reasons for premature discontinuation from the Treatment period, as recorded on the end of study discontinuation page of the electronic case report form (eCRF), will be summarized (number and percentage) by treatment group for the Safety Set. The subjects who completed the study are those that completed the final scheduled visit (Visit 6) at the end of the Treatment period.

In addition, the number and percentage of subjects who completed the study visits will be presented by visit for each treatment group and overall for the Safety Set.

All subjects who prematurely discontinued during the Treatment period will be listed by discontinuation reason for the Randomized Set.

Follow-up information, new (post-treatment) AEs and new (post-treatment) medication, will be listed for the Safety Set.

7. PROTOCOL DEVIATIONS

Protocol deviations and violations will be recorded by the site separately from the clinical database. The CRO/Shire will classify the protocol deviations and violations per the agreed protocol violation and deviation management plan. The Shire study team will review the protocol deviations and their classification throughout the study and before treatment unblinding and database lock.

Decisions of the review will include:

• Accuracy of protocol deviations and violations categorization.

For any criteria for protocol deviations that can be completely implemented by a computer program, the detailed algorithm will be agreed upon. Details of such algorithms will be included in the derived dataset specifications and finalized before treatment unblinding.

Confirmed protocol violations and protocol deviations will be documented in the Protocol Violation/Deviation tracker for the study. Protocol deviations/violations will be summarized by category and site for each treatment group (SHP465 6.25 mg and Placebo) and overall, for the Safety Set. Protocol deviations/violations will be listed for the Randomized Set.

Protocol SHP465-309

8. DEMOGRAPHIC AND OTHER BASELINE CHARACTERISTICS

8.1 Demographic and Other Baseline Characteristics

Descriptive summaries of demographic and baseline characteristics will be presented by treatment group (SHP465 6.25 mg and Placebo) and overall for the Safety Set and FAS.

Demographics and baseline characteristics will be examined to assess the comparability of the treatment groups at baseline, where baseline is defined as the last assessment prior to the first administration of the investigational product.

The following demographic characteristics will be summarized in the following order in the tables: age, sex, ethnicity, race, weight, height and body mass index (BMI). In addition, other baseline characteristics such as years since diagnosis of ADHD, ADHD Subtype, baseline ADHD-RS-5 total score, and baseline CGI-S will be summarized.

Age, weight, height, BMI, years since diagnosis of ADHD, ADHD-RS-5 total score will be summarized as continuous variables using number of subjects, mean and SD, median, and minimum and maximum values, while age (categorical), sex, ethnicity, race, and Baseline ADHD Subtype and CGI-S will be summarized as categorical variables using number of subjects and percentages for each category. All summarized values will be taken from the Screening Visit (Visit 1), except for baseline ADHD-RS-5 total score, baseline CGI-S, height, and weight. In addition, baseline weight and baseline height will be summarized in both conventional and international system of units.

Age will be calculated as the difference between date of birth (DOB) and date of informed consent (DINFC), truncated to months, using the following:

• Age = floor((intck('month',DOB,DINFC) - (day(DINFC) < day(DOB))) / 12)

BMI will be calculated using one of the following:

- Weight in pounds * 703 / (Height in inches)²
- Weight in kilograms / (Height in meters)²

Number of years since diagnosis of ADHD will be based on the date of informed consent. Demographics and baseline characteristics will be listed for the Safety Set.

In addition, demographics and baseline characteristics tables will be repeated by age group (6-8 years and 9-12 years).

8.2 Medical History

Medical history will be collected at the Screening Visit (Visit 1) and will be listed for the Safety Set.

The psychiatric diagnosis will be established with Mini International Neuropsychiatric Interview for Children and Adolescents (MINI-KID) at the Screening Visit (Visit 1) and will be listed for the Safety Set.

ADHD non-medication treatment history, behavioral therapy history, collected at the Screening Visit (Visit 1) will be listed for the Safety Set.

Protocol SHP465-309

9. EXTENT OF EXPOSURE AND TREATMENT COMPLIANCE

9.1 Exposure to Investigational Product

Exposure to double-blind investigational product for the Safety Set will be summarized by visit for each treatment group and age group. The following statistics will be calculated by visit for the investigational product:

- Days of dosing: number of days on which dose information was available and non-zero
- Total dose (mg) for SHP465: total number of capsules taken × dose level
- Average daily dose (mg/day) for SHP465: the total dose / total days of dosing
- Cumulative dose (mg) for SHP465: sum of total dose since start of treatment
- Duration of exposure in weeks: the total days of dosing / 7

An appropriate statistical summary will be applied to present for each of the above statistical quantities.

Subjects will be categorized in 1 week increments by their overall duration of exposure in days and will be presented using subject counts and percentages.

In addition, person-time (overall total exposure in days) will be derived for SHP465. It is calculated as total number of days in which SHP465 was taken for each subject (total days of dosing for the Treatment period), and then sum over all subjects for the Treatment period.

All dosing information, for example, total dose, average daily dose and cumulative dose, will be listed.

If a subject is lost to follow up without returning the leftover investigational product and without providing subsequent safety information, then the subject's dose information will be treated as missing. In particular, for subjects who are lost in the follow up after the Baseline Visit (Visit 2), it will not be assumed that any of the investigational products has been ingested unless there is a post-baseline safety assessment. Subjects who do not return the investigational product but return to the site for the following visit will have the dose return information entered into the database on the scheduled visit.

9.2 Measurement of Treatment Compliance

Investigational product dosing compliance during the treatment period is defined as the total number of capsules actually taken by a subject during that period divided by the total number of capsules expected to be taken during the same period multiplied by 100. The total number of capsules actually taken is calculated by the total number of capsules dispensed minus the number of capsules returned. If a bottle is not returned, the number of capsules returned for that bottle will be imputed to zero. The number of capsules expected to be taken is calculated as the number of days the subject was in the treatment period multiplied by the number of capsules to be taken per day during the treatment period. Compliance rates will be calculated separately for SHP465 6.25 mg and placebo.

Summary statistics for investigational product compliance will be presented by treatment group (SHP465 6.25 mg and Placebo) and by age group during the treatment period for the Safety Set. The investigation product treatment compliance will be categorized as <80%, 80-120%, or >120%. The category 80-120% is considered compliant. Categorical data will be presented for the Safety Set.

Calculated compliance data for each subject will be listed.

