7.1.1.3 Baseline Visit (Visit 2)

Once the screening central clinical laboratory tests and 12-lead ECG results have been obtained, in addition to repeat assessments (if required), and the subject has completed the required washout period (if applicable), the subject will return to the site for the baseline visit (Visit 2).

Inclusion/exclusion criteria must also be reviewed during this visit to ensure subjects continue to meet all eligibility criteria.

Table 1 outlines all procedures to be conducted during the baseline visit (Visit 2) with further clarification provided below:

- For subjects with >32 days since the safety measurements at the screening visit (Visit 1) were collected, an abbreviated physical examination, 12-lead ECG in triplicate, serum pregnancy test, urine drug screen, and all clinical laboratory tests must be repeated, and the results reviewed by the investigator prior to the subject being enrolled.
- Blood pressure and pulse will be collected 3 times (with approximately 2 minutes in between each collection) using the age-appropriate cuff during the visit.
- If >32 days since the screening visit, 3 ECGs will be taken, with approximately 3 minutes in between each one, to ensure appropriate baseline intervals are established. The investigator will perform the initial interpretation of the ECG immediately after collection to ensure the safety of each subject and to determine eligibility. The ECG tracing will be sent to the central reader for analysis. Upon review of the report from the central reader, the investigator will re-evaluate the clinical significance of the ECG in light of other safety data for the subject. If abnormal and significant results are observed following assessment by the central reader, the investigator, in consultation with the appointed CRO Medical Monitor, will confirm the subject's continued participation in this study.

Page 44

- The C-SSRS "since last visit" version should be completed.
- For eligible subjects, the investigator or assigned site staff designee will access the IWRS to enroll the subject and obtain an investigational product bottle number to dispense to the subject. Subjects will be dispensed a 9-count bottle of investigational product to cover them until their next regularly scheduled visit. Subjects will be instructed to take 1 capsule each day. Dosing will begin the morning following the baseline visit (Visit 2).

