7.1.2 Treatment Period

7.1.2.1 Treatment Period (Visits 3-5)

During the 4 weeks of treatment, visits will be scheduled every 7 days (±2 days) to assess safety and efficacy based on TEAEs, efficacy, and the dosing guidelines in Section 6.2.3.

Throughout the treatment period, subjects may attend the clinic for unscheduled visits to address any medical needs that arise between scheduled visits.

- Table 1 outlines all procedures to be conducted during Visits 3 to 5 and should serve as the primary point of reference regarding study procedures. Further clarification for these visits is outlined as follows: Subjects will be dispensed a 9-count bottle of investigational product to cover them until their next regularly scheduled visit. Subjects will be instructed to take 1 capsule each day. Dosing will begin the morning after each visit.
- Blood pressure and pulse will be collected 3 times (with at least 2 minutes in between each collection) during the visit. The average of each set of 3 measurements will be used to determine continued participation in the study (see Section 4.4.1).
- Scales should be completed by the same rater with input from the same parent/LAR whenever possible.
- The C-SSRS "Since Last Visit" Version of the Pediatric/Cognitively Impaired Version should be completed during the last treatment visit.

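### SAP 9.2 counts an unreturned 9-capsule bottle as fully taken where about 7 capsules were due, without saying whether the 9.1 non-return rules come first, so the compliance category can be wrong in either direction

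*SAP*

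**What the plan says.** SAP 9.2 defines compliance as capsules taken over capsules expected, times 100. Capsules taken are those dispensed minus those returned; capsules expected are the days in the treatment period times the daily number of capsules. For non-return it adds: "If a bottle is not returned, the number of capsules returned for that bottle will be imputed to zero". It then sets three categories, below 80%, 80-120% and above 120%, and states: "The category 80-120% is considered compliant".

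The supply figures come from the protocol. At baseline (Protocol 7.1.1.3), "Subjects will be dispensed a 9-count bottle of investigational product to cover them until their next regularly scheduled visit", and the same applies at Visits 3 to 5 (Protocol 7.1.2.1). In the treatment period, "visits will be scheduled every 7 days (±2 days"), with one capsule a day. Protocol 7.1 and footnote b of Table 1 in both documents measure the ±2 days from the baseline visit.

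SAP 9.1 has three rules of its own on non-return:

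- For a subject lost to follow-up who neither returns product nor gives later safety information, "then the subject's dose information will be treated as missing".
- For a subject lost after baseline, no capsules are counted as taken unless some safety assessment follows.
- For a subject who attends the next visit but leaves the product at home, a count is still recorded: "Subjects who do not return the investigational product but return to the site for the following visit will have the dose return information entered".

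Section 9.1 also uses a capsule count for dose: "Total dose (mg) for SHP465: total number of capsules taken", multiplied by the dose level. Section 9.2 does not refer to 9.1. The title of SAP 19.5 mentions the number of capsules, but its text deals only with a missing date of last dose.

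**The concern.** A bottle that does not come back tells us nothing about how many capsules were taken from it. Setting the returned count to zero turns that unknown into complete use of the bottle. Because each bottle carries two spare capsules at nominal spacing, it credits more than one capsule a day.

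In a fixed-dose trial, the compliance table is where a reader checks how much of the assigned dose was received. With about 30 subjects per arm, one misclassified child moves an arm's compliant percentage by 1/30 = 3.3 points. In an age-group table with about 15 per cell, the shift is 1/15 = 6.7 points.

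The missing precedence statement adds to this. For a subject lost to follow-up, 9.1 gives missing dose information or no assumed ingestion, while the 9.2 sentence taken alone gives 9 capsules taken. Two programmers could each follow the SAP and produce different tables.

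**Working it through.** **Inputs.** 9 capsules per bottle (Protocol 6.3.2); four bottles, dispensed at Visits 2, 3, 4 and 5, so 36 capsules; one capsule a day (Protocol 6.2.3); treatment period 4 weeks = 28 days (Protocol 3.2); compliant band 80-120% (SAP 9.2). The documents give no compliance figure to reproduce. As a check on the definition, a fully adherent child who returns every bottle has (36 − 8)/28 = 100.0%, as intended. All figures below apply to a bottle for which the 9.2 zero is actually used.

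**1. One unreturned bottle, nominal spacing, contents unknown.** Let x be the capsules taken from the other three bottles. The SAP value is (x + 9)/28. At one capsule a day, the truth lies between x/28 and (x + 7)/28.

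| x | SAP value | Possible range at one a day | SAP category |
|---|---|---|---|
| 13 | 22/28 = 78.6% | 46.4% to 71.4% | <80%, right |
| 14 | 23/28 = 82.1% | 50.0% to 75.0% | compliant, wrong |
| 15 | 24/28 = 85.7% | 53.6% to 78.6% | compliant, wrong |
| 16 | 25/28 = 89.3% | 57.1% to 82.1% | compliant, unknown |
| 21 | 30/28 = 107.1% | 75.0% to 100.0% | compliant, unknown |

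For x = 14 or 15 the category is wrong whatever the missing bottle held, provided no more than one capsule a day was taken. For x = 16 to 21 the true category cannot be known, yet the SAP always reports compliant. For x of 13 or fewer the category is right. The SAP value exceeds 100% only from x = 20 (29/28 = 103.6%).

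**2. One constructed case.** 21 capsules are taken in 21 days (Visit 5 on day 21), the fourth bottle is untouched and unreturned, and the last interval is d days. True value = 21/(21 + d); SAP value = 30/(21 + d).

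| d | True | SAP |
|---|---|---|
| 5 | 80.8% | 115.4% |
| 6 | 77.8% | 111.1% |
| 7 | 75.0% | 107.1% |
| 8 | 72.4% | 103.4% |
| 9 | 70.0% | 100.0% |

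The category is wrong for d = 6 to 9 and unchanged for d = 5.

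**3. Windows measured from baseline.** Visit 5 can fall on days 19 to 23 and Visit 6 on days 26 to 30, so the last interval can run from 26 − 23 = 3 to 30 − 19 = 11 days. Take full adherence up to Visit 5 and an untouched, unreturned fourth bottle:

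- Visit 5 on day 23, Visit 6 on day 26: true 23/26 = 88.5%; SAP (23 + 9)/26 = 123.1%. A compliant child is classed above 120%.
- Visit 5 on day 19, Visit 6 on day 30: true 19/30 = 63.3%; SAP (19 + 9)/30 = 93.3%. A child below 80% is classed as compliant.

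**4. Several unreturned bottles.** A fully adherent child with three unreturned bottles at nominal spacing has an SAP value of (7 + 27)/28 = 121.4%, against a true 100%.

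**5. Dose, only if 9.1 uses the 9.2 count.** In the d = 7 case, 30 × 6.25 = 187.5 mg would be credited against a true 21 × 6.25 = 131.25 mg.

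**The case against.** The best defence is that the two sections can be read in sequence. The first two 9.1 rules act on subjects lost to follow-up; the 9.2 zero acts on a bottle. On that reading, compliance is not calculated when dose information is missing, an entered count is used when there is one, and the zero is only a residual. A reader might infer that 9.1 and 9.2 flatly contradict each other. The documents do not support that: the sequential reading is possible, and what is missing is the statement that it applies.

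The 75.0%-to-107.1% case is also narrower than it looks. If the child attends Visit 6 without the bottle, Visit 6 can be read as the following visit at which 9.1 has return information entered. If the child does not attend, 28 days in the treatment period is not established. For exposure, SAP 19.5 replaces a missing last-dose date with the last visit at which product was returned; carried over to compliance, 21 days would give 30/21 = 142.9%, not a compliant value. If product was discontinued, Protocol 4.4 requires the total amount taken to be in the source documents. This case is an illustration, not a typical result.

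Non-return should also be uncommon. Protocol 6.4 makes the investigator responsible for retrieving supplies and requires discrepancies to be investigated, and Protocol 6.5 has parents bring product and packaging to every visit.

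These points limit how often the zero is used. They do not rescue it where it is used: step 1 for x = 14 or 15 needs no assumption about what the missing bottle held beyond one-a-day dosing. After Visit 6 the only scheduled contact is a telephone call, so no later site visit is planned at which the fourth bottle could be recovered.

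**Conclusion.** The point holds for any bottle to which the 9.2 zero is applied. The rule credits 9 capsules where about 7 were due and can misplace a child in either direction: below 80% reported as compliant (at most 75.0% or 78.6% reported as 82.1% or 85.7%), or compliant reported as above 120% (88.5% as 123.1%). The precedence between 9.1 and 9.2 is unstated.

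The figures assume no more than one capsule a day and, in steps 1 and 4, nominal spacing; steps 2 and 3 also assume an untouched fourth bottle. The number of unreturned bottles is unknown and may be small.

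A reader might infer that the efficacy conclusion is at risk. It is not: no analysis set, primary or key secondary model uses compliance. The effect is confined to the descriptive compliance output, where subject-level values are also listed, and reaches total, average daily and cumulative dose only if 9.1 uses the 9.2 count, which the SAP does not say. It is worth correcting because a stated rule gives a wrong answer and the correction is cheap.

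**What to change.** In SAP 9.2, delete the zero imputation and state the order:

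1. Use the count entered under 9.1, or the recorded total amount taken, where either is available.
2. Set compliance to missing where 9.1 sets dose information to missing.
3. Treat any remaining unreturned bottle as unknown, and calculate compliance under two bounds for that interval: 0 capsules, and the smaller of 9 or the number of days in the interval. The limit of 9 is needed because an 11-day interval would otherwise credit more than the bottle holds.

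Report the number of subjects with unreturned bottles and the number of such bottles by arm. Show the category table under both bounds only if any subject's category differs between them. State that the bounds assume one-a-day dosing and that over-use from an unreturned bottle cannot be assessed. Use the same capsule count for the dose quantities in 9.1.

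Applied to the examples: the d = 7 case becomes 21/28 = 75.0% to 28/28 = 100.0%, so both categories are shown. The day 23/26 case becomes 23/26 = 88.5% to 26/26 = 100.0%, compliant under both bounds. With x = 14 the range is 50.0% to 75.0%, below 80% under both.

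The cost is a few sentences of SAP text and a derivation change before unblinding. Affected subjects get a range instead of a single value.

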10. PRIOR AND CONCOMITANT MEDICATION

Version WHODRUG March 2017 of the WHO drug dictionary will be used to classify prior and concomitant medications by preferred term.

Prior medication is defined as any medication taken prior to the date of first dose of investigational product.

Concomitant medication is defined as any medication with a start date prior to the date of the first dose of investigational product and continuing after the first dose of investigational product or with a start date between the dates of the first dose and last dose of investigational product, inclusive.

Any medication with a start date after the date of the last dose of investigational product (post-treatment) will not be considered a concomitant medication.

Both prior and concomitant medication usage will be summarized separately by the number and percentage of subjects receiving each medication within each preferred term by treatment group (SHP465 6.25 mg and Placebo) and overall for the Safety Set. Medications can be counted both as prior and concomitant medication. Multiple medication usage by a subject in the same category will be counted only once for the purpose of the summaries.

For ADHD medication history collected at the Screening Visit (Visit 1), version WHODRUG March 2017 of the World Health Organization (WHO) drug dictionary will be used to classify ADHD medications by preferred term. ADHD medication history will be summarized separately by the number and percentage of subjects receiving each medication within each preferred term by treatment group (SHP465 6.25 mg and Placebo) for the Safety Set. ADHD medication history will be listed for the Safety Set.

All prior, concomitant and post-treatment medications will be listed for the Safety Set.

11. EFFICACY ANALYSES

All efficacy analyses will be performed using the FAS. All statistical tests will be 2-sided hypothesis tests performed at the 0.05 level of significance. All confidence intervals (CI) will be 2-sided 95% CIs, unless stated otherwise. Only post-baseline assessments from Visit 3 (Week 1) up to Visit 6 (Week 4) that were collected on or before 2 days after the last dose of double-blind investigational product will be analyzed.

